prot=g of protein consumed per day and pot=meqs of potassium consumed per day(19). The Short Physical Performance Battery (SPPB) is a well-characterized global measure of lower-extremity function and mobility. It will be assessed during screening (20, 21), at 3 and 6 months. The test consists of gait speed, chair stands, and balance; it is a strong predictor of disability and mortality in initially non-disabled older persons. SPPB scores of 4-9 have already been successfully used as a range associated with risk for developing mobility disability(21). The 400-meter walk is a measure of aerobic endurance where participants are instructed to complete the 400m distance (on a flat indoor surface) at their normal pace and the time to complete the walk is recorded in minutes and seconds. A comprehensive metabolic profile (CMP), including tCO₂, electrolytes, blood glucose and creatinine will be assessed at baseline and at 6-month follow-up. In conjunction with data from urine collections and analysis, CMP will allow calculation of fractional excretion of Na⁺, K⁺, Cl⁻, and the anion gap(22).

Bone Health. Because the kidney's capacity to excrete acid declines with age, acid-producing diets lead to a positive balance of protons and mild (often) subclinical acidosis. This acidic milieu facilitates release of Ca²⁺ from bone and increases bone turnover; it impairs osteoblast function and activates osteoclasts through stimulation of the proton-sensing receptor OGR1 and release of prostaglandin E2. Phosphate and bicarbonate released from bone mineral neutralize acid by a physicochemical reaction, leading to further Ca²⁺ release from the bone. In addition, renal Ca²⁺ excretion increases, through suppression of Ca²⁺ transporters and the calcium-sensing receptor (CaSR), which is exquisitely pH sensitive. CaSR regulates both renal Ca²⁺ absorption and parathyroid hormone release. Since a dietary acid load does not alter intestinal Ca²⁺ absorption, negative Ca²⁺ balance persists as long as the proton balance remains positive (33-73). This pathophysiologic mechanism explains why it is of great interest that we evaluate bone density in our study, which is testing the feasibility of neutralizing diet-dependent acid load in the elderly.

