collection of these data throughout the study. The first recall will be conducted at the SV to review all procedures and tools to be used. A “Food Amounts” booklet containing 2-D visual portions will be provided to the participant for use in standardizing portion sizes. Subsequent recalls will be conducted by telephone with trained interviewers from the CRU placing unscheduled telephone calls to participants at seven additional timepoints. When contacted by the staff, subjects will be asked to recall and report their dietary intake from the previous day’s 24-hour period. In addition to the first in-person SV recall, telephone recalls will be done within one week of the SV (1) to further assess eligibility (an average of both protein intake and K+ will be used to calculate the NEAP score), and within a 1-week period of each follow-up visit for a total of eight recalls during the study. Recalls will be randomly scheduled and will reflect both weekday and weekend intakes.

At the baseline visit and remaining in-clinic follow up visits, participants will spend approximately 4hr in the Clinical Research Unit (CRU), have their physical ability tested (FV2 and FV3 only), have blood drawn for blood gas analysis as well as blood for cystatin c and blood for storage. The blood gas draw will be performed in the CRU. Urine will be collected over the 4hr period (this is necessary because urine collections need to be monitored and refrigerated). Participants will be encouraged to take 500 ml of water during their stay at the CRU, to stimulate urine production. During these visits (not at FV2) the participants will also provide information about their dietary habits using the VioFFQ™ (Viocare, Inc., Princeton, NJ), which is a validated, web-format system for collecting food frequency data on a subject’s dietary behavior and food use patterns. The questionnaire will be self-administered. Participants will also receive a DXA scan of their hip at BV and FV3.

Table showing Study Schedule of events	SV	BV	FV1	FV2	FV3
Location of Visit	CRU	CRU	Phone Call	CRU	CRU
Study Week Number Activity/Assessment	-1 wk	0	1 mo	3 mo	6 mo
Informed Consent	X				
Cognitive Screen (MoCA)	X				
Fasting blood draw (CMP)	X			X	X
Urinalysis (Spot Urine)	X				X
SPPB	X			X	X
400m walk test		X		X	X
VITALS	X	X		X	X
DXA		X			X
24-hour Diet Recall to calculate NEAP	X		X	X	X
Medical History and Medications	X		X	X	X
Food Frequency		X			X
Blood Gas, Cystatin C, blood for storage		X			X

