4hr urine collection to determine (Net acid excretion (NAE); urinary nitrogen and Ca ⁺² excretion, uACR) Urea Nitrogen, Uric Acid, Urine Creatinine,) and obtain urine for storage		X		X	X
Randomization		X			
Urine Metabolomics		X			X
Dispense Medication		X		X	
Medication Adherence				X	X

Outcome Measure(s)

1. Determine the feasibility of achieving ~50% reduction in net acid excretion (NEA/Cr meq/g) following 6 months of oral bicarbonate supplementation, compared to the placebo group
2. Determine
 - a. Recruitment yields
 - b. Adherence to the assessment schedule
 - c. Compliance with intervention over 6 months

- d. Collect data on variability and longitudinal correlation structure of kidney function, lean body mass and functional outcomes
- 3. Ascertain feasibility of using metabolomics to detect changes in kidney function following the intervention

Analytical Plan

All data will be entered as collected into web-based forms; analysis datasets will be stored in SAS. All data will be examined monthly by histograms and scatterplots to check for internal inconsistencies, unusual data needing further verification, and outliers. In few case of outliers and unusual data, participant's charts were reviewed to ascertain whether any adverse measurement conditions or circumstances or potential artefacts existed. Only in cases where measurement artefacts were identified or other circumstances were found that adversely affected data collection were the measurements removed. Otherwise all data remained within the data set. Sensitivity analyses will be performed with and without potential outliers included in individual analyses.

For each analysis, regression diagnostics and exploratory analyses will be performed to find appropriate transformations of the variables, if needed. Priority in choosing a transformation will be to satisfy: 1) linearity, 2) homogeneity, and 3) normality assumptions. Initial analyses will follow the "intent-to-treat" principle. Due to having low power to detect potentially important relationships within this pilot, emphasis will be on using confidence intervals to described estimated parameters and relationships. When hypothesis testing is performed, we will set the significance level at $\alpha=0.05$. We have chosen this level for all hypothesis tests within the pilot because risk of missing an association by making a Type II error outweighs the concern for falsely identifying relationships via a Type I error.

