Aim 1 Determine the feasibility of achieving ~50% reduction in net acid excretion (NAE/Cr meq/g) by the kidney after 6-months of oral bicarbonate supplementation vs. placebo. (NAE/Cr was measured at each visit.)

We will use mixed effects analysis of covariance (ANCOVA) to estimate change in NAE/Cr within randomized groups, including the baseline value of NAE/Cr and the intervention effect in the model. A contrast will be used to obtain estimates and 95% confidence intervals after 6-months. This approach utilizes all measurements obtained during follow-up and can provide unbiased estimates, if missing outcomes are related to outcomes obtained at other time points.

Aim 2 Ascertain recruitment yields, adherence to the intervention, adherence to the assessments, and sustainability of the intervention over 6 months; and collect data on variability and longitudinal correlations in kidney function, lean body mass, and functional outcomes to design a future full-scale clinical trial.

For recruitment yields, we will calculate the proportion of screened participants randomized, overall, and within gender and ethnic subgroups.

Adherence to the intervention will be measured as the proportion of the prescribed dose (bicarbonate or placebo) taken, based on pill counts.

Compliance with assessments will be determined by calculating proportion lost to follow-up at each visit and the percent of missing measurements.

Sustainability of the intervention will be assessed via: a) generalized estimating equations for repeated measures on the proportion of expected pills a participant took.

Means (proportions), variances, and 95% confidence intervals (exact CI where needed) will be calculated within intervention groups and for the difference between groups for all endpoints.

Correlations coefficients (both Pearson and Spearman) will be used to investigate the association between net endogenous acid production (NEAP) and other measures of interest, as well as changes in net acid excretion

(NAE) and measures of interest. (Measures of interest: tCO₂, blood bicarbonate (blood gas), eGFR, urineACR, SPPB, 400m walk, bone density).

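### Specify a baseline-adjusted between-arm interval for the continuous endpoints that have a baseline value, as the plan already does for NAE/Cr

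*Combined protocol and SAP*

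**What the plan says.** Aim 1 of the Analytical Plan analyses NAE/Cr by a mixed-effects analysis of covariance, "including the baseline value of NAE/Cr and the intervention effect in the model".

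For the other endpoints, Aim 2 says that means or proportions, "variances, and 95% confidence intervals (exact CI where needed) will be calculated within intervention groups and for the difference between groups for all endpoints". It names no model or covariate, and does not say whether the means are of follow-up values or of changes from baseline. Nothing elsewhere extends the Aim 1 model to these endpoints. The general statement "For each analysis, regression diagnostics and exploratory analyses will be performed to find appropriate transformations of the variables, if needed" concerns transformations and names no baseline term.

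The general part of the Analytical Plan concedes low power and says that "emphasis will be on using confidence intervals to described estimated parameters and relationships".

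Baseline values are collected:

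- SPPB: "It will be assessed during screening (20, 21), at 3 and 6 months".
- DXA: "Participants will also receive a DXA scan of their hip at BV and FV3".
- Metabolic profile, which includes tCO₂: "blood glucose and creatinine will be assessed at baseline and at 6-month follow-up". The schedule table places the first draw at the screening visit and adds one at 3 months.
- Cystatin C, blood gas and the 4-hour urine that gives uACR: marked at the baseline visit in the table.
- 400 m walk: marked at the baseline visit in the table, but the text above the table confines physical testing to the 3- and 6-month visits.

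**The concern.** The plan makes confidence intervals its main product, so their width matters. For a measure that tracks within a person, much of the spread in a follow-up value is stable difference between people that the baseline value already explains. A comparison that ignores baseline leaves this spread in the interval. It also lets a chance difference between arms at baseline carry through to the reported difference. The plan avoids both for NAE/Cr but does not say that it will for kidney function, bicarbonate, physical function or DXA.

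At stake is the precision of the between-arm estimates for the measures named as possible endpoints of the full-scale trial.

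**Working it through.** **Inputs from the documents.** 35 per group remaining at 6 months, two-sided 5% level, 80% power, difference of 11.4 mEq/g, and 16.5 mEq/g (Sample Size section and the power analysis in the Analytical Plan). The 16.5 is worded as a change, but the power figure works only if it is read as a standard deviation.

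**Assumed.** The baseline-to-6-month correlation ρ is not given; I use 0.3 to 0.9. I also assume equal SD at baseline and follow-up.

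**The plan's own figure.** Standard error = 16.5 × √(2/35) = 16.5 × 0.239 = 3.94. Noncentrality = 11.4/3.94 = 2.89. Power by the noncentral t distribution is 81.3%, against the stated 80%; the difference detectable with 80% power is 11.2. Randomised number: 70/(1 − 0.125) = 80. The figure reproduces. It is the only between-arm precision figure in the documents, and it concerns NAE/Cr.

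**95% CI half-width for the other endpoints, in SD units, 35 per arm.**

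- Follow-up means: t(0.975, 68) × √(2/35) = 0.477 at any ρ.
- Mean changes: 0.477 × √(2(1 − ρ)).
- Baseline-adjusted: t(0.975, 67) × √(2/35) × √(1 − ρ²) × √(1 + 1/66). The last factor is the small cost of estimating the slope.

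| ρ (assumed) | Follow-up means | Changes | Adjusted | Follow-up means wider by | Changes wider by |
|---|---|---|---|---|---|
| 0.3 | 0.477 | 0.564 | 0.459 | 4% | 23% |
| 0.5 | 0.477 | 0.477 | 0.416 | 15% | 15% |
| 0.7 | 0.477 | 0.369 | 0.343 | 39% | 8% |
| 0.8 | 0.477 | 0.302 | 0.288 | 65% | 5% |
| 0.9 | 0.477 | 0.213 | 0.210 | 128% | 2% |

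**Chance imbalance.** The baseline difference between arms has SD √(2/35) = 0.239. P(|Z| > 0.3/0.239) = 0.21, so an imbalance above 0.3 SD is expected in about 21% of such trials. At ρ = 0.9, an imbalance of 0.3 SD shifts the difference in follow-up means by 0.9 × 0.3 = 0.27 SD.

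**Coverage.** In 40,000 simulated trials at each of ρ = 0.5, 0.7 and 0.9, the unadjusted interval for follow-up means covered the true difference 94.9% to 95.1% of the time. Among the trials with imbalance above 0.3 SD, coverage was 89%, 84% and 78% respectively.

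**The case against.** **The sentence may be descriptive.** It covers every endpoint, which on its face includes NAE/Cr, and NAE/Cr also has its own model. It therefore need not exclude further modelling. This stands in part: the plan states no decision to ignore baseline. But the interval for the group difference is the only between-arm analysis it gives for these endpoints.

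**Changes may be meant.** The hypothesis is about decline, and the protocol often speaks of change. If so, the gain from adjustment is small at high correlations. This stands, and both readings are shown above.

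**The correlations are unknown.** Estimating them is one of the pilot's tasks. Eligibility also limits eGFR to 30–89, SPPB to above 3 and serum bicarbonate to at most 30, and a restricted range tends to lower a correlation. This stands: no single size can be claimed, and one value need not fit all the endpoints.

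**A reader might infer that the planned intervals are biased or invalid.** They are not. Coverage over all randomisations is nominal, and chance imbalance is already allowed for in their width. The lower coverage above is conditional on a large imbalance having occurred.

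**A reader might infer that the future trial's planning inputs are lost.** They are not. Aim 2 already collects variances and longitudinal correlations, and the residual SD for an adjusted analysis follows as SD × √(1 − ρ²). Nor does adjustment improve the relative precision of an SD estimate, which is about 1/√(2 × 68) = 8.6% here.

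**Conclusion.** This is a nearly free improvement, not an error. For the continuous endpoints with a baseline value, the plan gives a between-arm interval without baseline adjustment, although it adjusts NAE/Cr and puts its emphasis on intervals. The cost is precision. It ranges from negligible (4% at a correlation of 0.3, follow-up means; 2% at 0.9, changes) to large (128% at 0.9, follow-up means). These sizes rest on 35 per arm, equal SDs and assumed correlations.

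A reader might infer that every outcome except NAE/Cr is affected, or that the intervals are far wider than necessary. The documents support neither. Recruitment yield, pill adherence and retention have no baseline value, and pill-taking over time has its own repeated-measures model. Large excess width requires both that follow-up means are compared and that the correlation is about 0.8 or more; the plan states neither.

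The 400 m walk belongs with the other endpoints only once the conflict over its baseline measurement is resolved.

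**What to change.** In the Aim 2 part of the Analytical Plan, state that for eGFRcys, uACR, tCO₂, blood bicarbonate, SPPB, DXA measures and the 400 m walk, the between-arm estimate and 95% CI come from the Aim 1 type of model: follow-up value on arm and the participant's own baseline value, with visit added where there is more than one follow-up. Use a log scale for uACR if the planned diagnostics call for it. With baseline in the model, the arm difference is the same whether the outcome is entered as a follow-up value or as a change, so this also settles that ambiguity.

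Keep the unadjusted means, variances and longitudinal correlations as description and as planning inputs. Leave recruitment yield, pill adherence and retention as they are. Reconcile the text and the schedule table on whether the 400 m walk is done at the baseline visit.

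The cost is a sentence in the plan and a few lines of SAS. No new data, visits or participants are needed.

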Official Title: Dietary Acid Load, Kidney Function and Disability in Elderly

NCT02691663

Date IRB-Approved: 6/27/2018

Study Title: Dietary acid load, kidney function and disability in elderly

Principal Investigator [name], **Co-investigator(s):** [name], [name], [name], [name]

Sponsor or funding source: (NIH/NIA and the Translational Science Center at Wake Forest University)

Background, Rationale and Context

Physical decline and frailty result from age- and disease-related impairments in organs and tissues. Frailty research has focused on the musculoskeletal, neurological and circulatory systems; yet interventions targeting these systems had limited success in preventing and treating functional decline. Given the aging of the US population, additional avenues for intervention development are urgently needed.

Fragility and disability in people ≥ 65 strongly correlate with declining kidney function and are evident even in early stages of chronic kidney disease (CKD)(1, 2). Moreover, CKD is highly prevalent in the elderly and associates with sarcopenia, osteopenia, and increased incidence of fractures/falls with hospitalization. Low serum bicarbonate and impaired acid-base homeostasis, also common in CKD, are increasingly appreciated as contributors to functional decline with advancing age(3-6). With aging, the adaptive response of the kidney to low serum bicarbonate and high metabolic acid load becomes maladaptive, facilitating CKD progression. Conversely, in adult patients with CKD, maintenance of serum bicarbonate at 24 meq/L with oral bicarbonate supplementation or increased consumption of base-forming foods slows CKD progression(7).

We proposed the current study and protocol based on the evidence summarized above and our preliminary studies, which suggest that: (1) In the Health Aging and Body Composition cohort (age 70-79) lower dietary acid load associates with stable kidney function over a 7-year follow-up, independent of age, race, gender, BMI, diabetes, hypertension or smoking status(8); (2) metabolomics analysis in participants of the African American Diabetes Heart Study suggested that it is feasible to segregate a urine metabolomics profile in the early stages of CKD (stages 2 and 3), and that lower consumption of base-forming fruits and vegetables and higher rates of acid excretion may be associated with CKD and its progression(9).

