Based on published studies(11-14), we have assumed a 6-month change in NAE/Cr within groups of 16.5 mEq/g. Assuming a conservative 12.5% loss-to-follow-up at 6 months (35 participants/group), we will have 80% power to detect a difference between groups in NAE/Cr as small as 11.4 mEq/g with a two-sided, Type I error rate of 0.05. Considering that expected change in NEA/Cr will be about 20-30 meq/d(11, 12, 14), we should be able to detect clinically important changes in NEA/Cr from the proposed intervention. For Aim#2, we are interested in estimating recruitment yields, compliance and other parameters that will inform the feasibility of a full-scale trial. With up to 83 participants recruited, we will be able to estimate the two-sided, 95% Clopper-Pearson Exact confidence interval with a width of 0.043 if the recruitment yield is 10%, and a width of 0.14 if the recruitment yield is 40%. For correlational analyses, 83 participants will allow us to detect correlation coefficients of 0.31 or larger with at least 80% power assuming a 2-sided 0.05 □.

Interventions and Interactions

Patients will be screened over the phone and in the clinic to see if they meet qualifications for the study. Once screened, they will be randomized into one of two groups- taking an oral bicarbonate supplement or a placebo.

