Power analysis: Based on published studies, we have assumed a 6-month change in NAE/Cr of 16.5 mEq/g within groups. Assuming a conservative 12.5% loss-to-follow-up at 6 months (35 participants/group remaining), we will have 80% power to detect a difference between groups in NAE/Cr as small as 11.4 mEq/g with a two-sided Type I error rate of 0.05. Considering that expected change in NEA/Cr will be about 20-30 meq/d we should be able to detect clinically important changes in NEA/Cr from the proposed intervention. For correlational analyses, 80 participants will allow us to detect correlation coefficients of 0.31 or larger with at least 80% power assuming a 2-sided 0.05 □.

Other Exploratory/Sensitivity Analyses:

Do NEAP and NAE correlate at baseline, when controlled for kidney function and caloric intake?

Do NAE and calcium excretion correlate at baseline and other time points, when controlled for kidney function and calcium intake?

Do NAE and sodium intake correlate? Do NAE and sodium excretion in the urine correlate? (An important one, if so, we will need to treat sodium intake as a confounder. There is physiological feasibility that these two may correlate.)

Does NEAP calculated from food recalls correlate with NEAP calculated from FFQs?

Human Subjects Protection

Human Subjects Involvement and Characteristics

We plan to recruit and randomize up to 83 older men and women who meet the inclusion/exclusion criteria described above. Participants will be randomized to bicarbonate capsules or placebo for 6 months. All assessments will be conducted during following visits and phone calls: screening phone call, 1 screening visit (SV1); 1 baseline visit (BV1); 1-month phone call, 3-months mid-intervention follow-up visit (FV1); and 1 post-intervention follow-up visit at 6-month (FV2).

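### The Aim 2 correlations of NEAP with kidney, functional and bone measures are planned without adjustment for age or sex, which could inflate or mask these exploratory associations (minor)

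*Combined protocol and SAP*

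**What the plan says.** The Aim 2 part of the Analytical Plan describes the method as follows: "Correlations coefficients (both Pearson and Spearman) will be used to investigate the association between net endogenous acid production (NEAP) and other measures of interest". The measures are tCO2, blood bicarbonate from blood gas, and "eGFR, urineACR, SPPB, 400m walk, bone density". No covariate, partial correlation or regression model is attached to these pairs, and no time point is given. The general paragraphs of the Analytical Plan cover transformations, diagnostics and outliers, but not confounding.

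Two other places treat similar associations differently:

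- The Background reports the preliminary cohort finding, which linked lower dietary acid load to stable kidney function, as "independent of age, race, gender, BMI, diabetes, hypertension or smoking status".
- Under Other Exploratory/Sensitivity Analyses, one question is "Do NEAP and NAE correlate at baseline, when controlled for kidney function and caloric intake". The pair of NAE and calcium excretion is likewise controlled, for kidney function and calcium intake. Sodium intake is to be handled as a confounder if it turns out to correlate with NAE.

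Power for correlations is stated twice. The Sample Size section says "83 participants will allow us to detect correlation coefficients of 0.31 or larger with at least 80% power"; the power analysis in the Analytical Plan says "80 participants will allow us to detect correlation coefficients of 0.31 or larger with at least 80% power". Both are two-sided at 0.05.

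**The concern.** NEAP is computed from the ratio of reported protein intake to reported potassium intake. It is observed, not assigned, so its correlations with other measures are observational even though they sit inside a randomised trial. The sample includes both sexes, and the age criterion is 65 and over with no upper limit. Age and sex are plausibly related to eGFR, walking performance and bone density, and they may also be related to what people eat. A crude coefficient mixes any relation between diet and outcome with these differences, in either direction.

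What is at stake is how these secondary coefficients can be interpreted. In particular, a crude NEAP-eGFR correlation could not be set beside the preliminary cohort result, which was reported as independent of age, race, gender and BMI among other factors. Masking matters too, because the Analytical Plan says that in this pilot it is more worried about missing an association than about finding a false one.

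**Working it through.** **Inputs from the documents.** r = 0.31; n = 83 (Sample Size) or n = 80 (Analytical Plan, power analysis); two-sided alpha 0.05; 35 per group, so 70 in total, expected at 6 months.

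**Inputs that are assumptions.** The documents give no correlation of age or sex with NEAP or with any outcome. I take a = 0.1 to 0.3 for confounder with NEAP, and b = 0.3 to 0.5 for confounder with outcome.

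**Formulas.** The power figures use Fisher z and apply to Pearson coefficients.

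- Test statistic mean: λ = atanh(r) × √(n − 3 − k), where k is the number of covariates.
- Rejection probability: Φ(λ − 1.96) + Φ(−λ − 1.96).
- Correlation induced by one confounder when the true partial correlation is 0: r = a × b.
- Crude correlation when the partial correlation is ρ: r = ρ × √((1 − a²)(1 − b²)) + a × b.

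**Step 1: reproduce the plan's figure (k = 0).** atanh(0.31) = 0.3205.

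- n = 80: λ = 0.3205 × √77 = 2.813, power 80.3%.
- n = 83: λ = 0.3205 × √80 = 2.867, power 81.8%.

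Both statements of at least 80% hold for crude correlations.

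**Step 2: false association.** The induced r runs from 0.1 × 0.3 = 0.03 to 0.3 × 0.5 = 0.15. With no true association and n = 83:

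| Induced r | Chance of p<0.05 |
|---|---|
| 0.03 | 5.8% |
| 0.05 | 7.3% |
| 0.08 (0.2 × 0.4, midpoint) | 11.1% |
| 0.10 | 14.6% |
| 0.15 | 27.2% |

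A simulation at n = 80 with a = b = 0.3 (induced r = 0.09; 20,000 runs) gave 12% for the crude test, in line with the formula's 12.4%, and about 5% after adjustment.

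**Step 3: masking.** Take ρ = 0.31, a = 0.3 and b = −0.3. The crude r is 0.31 × 0.91 − 0.09 = 0.192. At n = 80 the chance of detecting it is 40%, against about 80% for the partial correlation (79.8% with one covariate).

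**Step 4: cost of adjusting, as power at r = 0.31.**

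| n | Crude | Age and sex (k = 2) | Plus BMI (k = 3) |
|---|---|---|---|
| 83 | 81.8% | 80.8% | 80.3% |
| 80 | 80.3% | 79.3% | 78.7% |
| 70 (6-month completers) | 74.7% | 73.4% | 72.7% |

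Age and sex cost about one point. At n = 80 that already falls just under the stated 80%. If 6-month data are used, power is below 80% before any adjustment.

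**The case against.** The strongest reply is that these are descriptive correlations in a feasibility pilot. The plan speaks only of association, emphasises confidence intervals, acknowledges low power and openly accepts Type I error. The coefficients are not in the outcome list. Much of this stands and limits the weight of the point. It does not remove it: a confidence interval around a confounded coefficient is centred on the wrong quantity, and accepting Type I error is no answer to masking.

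Four stronger readings are tempting and are not supported:

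- **A reader might infer that the coefficients will be presented as effects of dietary acid.** The study's hypothesis is causal, but the Aim 2 text does not say this.
- **A reader might infer that they will select endpoints for the full-scale trial.** What the documents assign to that purpose is feasibility data and the variability and longitudinal correlation of kidney function, lean mass and functional outcomes. The NEAP correlations are given no such role.
- **A reader might expect very large error rates.** Induced r = 0.20 would give 44% rejection at n = 83, but that lies outside the single-confounder range assumed here. A second confounder could offset the first as easily as add to it. The entry requirement of NEAP above 40 mEq/d also restricts the range of NEAP and would tend to weaken its correlation with demographics.
- **A reader might want BMI-adjusted coefficients as the main result.** That is debatable. Proportional scaling of total intake cancels in a protein-to-potassium ratio, so body size is the weakest of the candidate confounders. BMI also partly reflects lean mass, which the study hypothesises is affected by acid load, so adjusting for it could remove part of the relation of interest.

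The documents' own precedents do not fix a covariate set either: the Background lists seven factors, and the exploratory questions use kidney function with caloric or calcium intake. Age and sex are a minimal choice, not one dictated by the text.

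**Conclusion.** The point holds as a minor one. The seven NEAP correlations are planned as crude coefficients, nothing elsewhere in the plan adjusts them for age or sex, and the documents control for covariates in comparable associations. Confounding could inflate or mask them. How much cannot be determined from the documents: under the assumed single-confounder range, false-positive rates at n = 83 run from close to nominal (about 6%) to about 27%, and opposing confounder correlations of 0.3 would reduce a partial r of 0.31 to about 0.19. The case is plainest for eGFR, walking and bone density; no specific confounding route is argued here for tCO2 or blood bicarbonate. The randomised Aim 1 comparison of NAE/Cr does not depend on any of this.

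**What to change.** In the Aim 2 paragraph on correlations, add that partial Pearson and partial Spearman coefficients adjusted for age and sex, with 95% confidence intervals, will be reported beside the crude coefficients. Add a version that also includes BMI as a sensitivity analysis, and describe all of them as observational associations.

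This takes one or two sentences and no new data: age and BMI are used for eligibility, and recruitment yield is already to be tabulated by gender. The price is the small power loss shown in the working. The power statement should give the figure for the adjusted coefficients, since the 80% claim is narrowly missed at n = 80, and should use one sample size where the document now gives both 80 and 83. Because the crude coefficients stay in the report, nothing now planned is lost.
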